4.2.3 EXPLORATORY ENDPOINTS

Participant use of anxiolytic medications will be assessed through both medical record review of prescriptions and patient reported use. All participants will record their use of any of the following medications: alprazolam, bromazepam, chlordiazepoxide, clonazepam, clorazepate, diazepam, flurazepam, and lorazepam. All participants will be given a TLFB measure to track daily use of anxiolytics during the course of the study. This will be administered weekly via a HIPAA secure REDCap link sent to his or her email. Participants who do not complete the weekly TLFB report in REDCap will be contacted by study staff in order to administer the recall via telephone. The TLFB is a reliable measure of patient-reported substance use (i.e., cigarettes, cannabis, and alcohol). Additionally, we will assess health related quality of life using the FACT-HN and symptom burden using the MSAS-SF. These measures will be included in exploratory analyses of the impact of the intervention on health-related quality of life and the impact of symptoms. Symptom presence may be included as a potential covariate in outcome analyses.

5 STUDY ENROLLMENT AND WITHDRAWAL

5.1 PARTICIPANT INCLUSION CRITERIA

In order to be eligible to participate in this study, an individual must meet all of the following criteria:

1. Provision to consent to the study procedures.
2. Stated willingness to comply with all study procedures and be available for the duration of the study.
3. Be aged 18 – 100.

4. Ability to read and communicate in English.
5. A confirmed malignancy of the head and neck region (including metastases from other primary tumors and cancers of unknown primary).
6. Initiation of RT at the University of Colorado Cancer Center.
7. Psychiatric and cognitive stability as assessed by chart review (i.e., no documented dementia diagnosis or unmanaged psychiatric symptoms) and study personnel (i.e., ability to attend to meeting with study personnel).
8. Ability to meet remotely via internet connection or over the phone.

5.2 PARTICIPANT EXCLUSION CRITERIA

An individual who fails to meet any of the inclusion criteria will be excluded from participation in this study. Mental health providers involved in this study may also use clinical judgment regarding appropriateness of participant for study (e.g., psychiatrically unstable).

5.3 STRATEGIES FOR RECRUITMENT AND RETENTION

We will recruit approximately 72 patients at the University of Colorado Cancer Center who are initiating radiotherapy (RT) for a cancer of the head and neck. This will include patients with a confirmed malignancy of the head and neck region, from clavicle to skull. This will include patients with diagnoses that include skin, thyroid, oral cavity, pharynx, larynx, paranasal sinuses and nasal cavity, salivary glands, unknown primary and metastases from other primary tumors. Participants will be initially screened for eligibility via chart review. MRNs and PIDs will be used to create a key, and then screen participants in EPIC using this key. The study team will retain this key in a separate file from the main database until data collection is complete. The study research assistant will screen patients for eligibility and will communicate with the radiation charge nurse regarding patient eligibility. [name], licensed clinical psychologists, will review questions or concerns about participant eligibility for mental health reasons. Eligible participants will be contacted for consent following their initial visit with a radiation oncologist. A study research assistant will communicate eligibility to the patient's treating radiation oncologist and obtain permission to approach from the treating physician. The study research assistant will then call the patient to assess interest via telephone. The patient can consent to study participation then or schedule a later time for consent with the research study assistant. There will be two possible routes for consent: Participants may provide verbal consent for screening and baseline procedures only and will provide a signed full consent prior to other study procedures (in person or via e-consent). The other route, participants will provide informed consent and authorization for the entirety of the study at the time of screening/baseline through an e-consent process. Signatures may be obtained via REDCap, mail, e-mail with scanned

document or picture of the signed consent, or by bringing the signed consent and authorization into the clinic.

Following consent, the participant will provide contact information to the study research assistant who will remain in contact with the participant. The research assistant will coordinate intervention and assessment sessions as necessary. Study data will be collected via email link connected to a secure REDCap database. These assessments can also be conducted in clinic via electronic tablet, or by phone if necessary. This will be coordinated by the study research assistant.

Given that patients with HNC are a highly distressed population, it is likely that some of the participants in this study will have a history of anxiety and depression as well as current symptomatology. Patients who are psychiatrically unstable or have cognitive impairment will be excluded from participation as determined by chart review and/or assessment of study personnel. All participants in the study will have access to all psychosocial supports available at UCCC including social work and clinical psychology.

All study participants will be provided with an MP3 player that they will be allowed to keep as part of study participation. Participants in the treatment as usual group will receive it at the end of study participation. Further, participants who participate in the qualitative interviews will receive a \$25 gift card in compensation for their time.

5.4 PARTICIPANT WITHDRAWAL OR TERMINATION

5.4.1 REASONS FOR WITHDRAWAL OR TERMINATION

Participants are free to withdraw from participation in the study at any time upon request. The study investigators may terminate the participation of participants who display inappropriate or disrespectful behavior toward the study personnel.

5.4.2 HANDLING OF PARTICIPANT WITHDRAWALS OR TERMINATION

Participants will be informed in the consent process that they may discontinue the study at any time.

5.5 PREMATURE TERMINATION OR SUSPENSION OF STUDY (STUDY STOPPING RULES)

As previously stated, the anticipated risks of study participation are low. However, if the study personnel believe at any point that participation in the study is detrimental to the

participant's health, participation will be suspended and the participant will be connected with mental health resources at the University of Colorado Cancer Center.

6 STUDY AGENT

6.1 STUDY AGENT(S) AND CONTROL DESCRIPTION

The study agent used in this trial is GI. GI is a relaxation technique involving the visualization of images and is considered an adjuvant cancer therapy (26). The GI intervention will include direct, written, and audio delivery of one of three GI vignettes. The patient will be able to choose one of the three vignettes. The vignettes are sourced, with permission (31) from the University of Michigan Comprehensive Cancer Center's Guided Imagery Library. The approximately twelve-minute-long vignettes included in the study will be: *Taking a Walk*, *Healthy Cell Alliance for Treatment*, and *Daily Intention* (32). Each vignette is similar in length and structure and relies on the same mechanisms of relaxation and bringing images to mind. After being randomized to the intervention participants will receive their first intervention exposure session before their scheduled CT simulation. After the initial session, the participant will be given an iPod shuffle on which their intervention material will be recorded. They will then receive a second, in person, intervention exposure during the first week of RT. The intervention, based on established psychotherapy principles, can later be self-administered both before and during RT.

A master's level therapist (i.e., psychology doctoral student, licensed clinical social worker, etc.) will deliver the GI intervention. Each study therapist will attend a training session either in person or virtually (via telephone/video conference) that will provide an introduction to the intervention, a review of each session component, and an opportunity to participate in role-play exercises to ensure facility in delivering the therapy. All training materials will be made available to the study therapists for continued review. Supervision will be provided to each study therapist as needed by [name].

The control or treatment as usual condition will include an orientation to RT from the clinic nurse coordinator. This will include a tour of the treatment room and education about RT. Patients will also receive educational materials about RT including the process of RT and CT simulation, treatment side effects, pain management, and swallowing exercises. Participants in this condition will also have access to psychosocial support resources (i.e., clinical psychologists and social workers) at UCCC. Patient use of these services during the study period will be monitored through chart review.

7 STUDY PROCEDURES AND SCHEDULE

7.1 STUDY PROCEDURES/EVALUATIONS

Following consent and completion of baseline measures, the participant will be randomized to either the intervention or treatment as usual condition. The research study assistant will coordinate the scheduling of the two intervention sessions for participants in the GI condition. Administration of the study measures will occur online, via REDCap. Participants will be offered the opportunity to begin/complete the survey at the cancer center on a provided tablet, but may also complete the survey in its entirety at home on their own personal internet-connected device.

All participants will complete assessments at baseline, following initiation of RT (during Week 1 of treatment), approximately halfway through RT (during Week 3 of treatment), at the end of RT (during Week 7 of treatment), and one month following completion of RT (around Week 12 after beginning treatment). Patients may complete the assessments listed any time during the specified week (7 days) of treatment, with Day 1 being defined as the first day of radiation treatment. Each session will also be recorded and reviewed for fidelity to the intervention. Study measures include the following:

- I. Anxiety and depression
 - a. The Hospital Anxiety and Depression Scale (HADS; [33]) is a 14-item self-report measure of anxiety and depression symptoms for use in medically ill patients, as it does not include the somatic symptoms of anxiety and depression that confound the assessment of distress in medically ill patients, and has demonstrated high reliability and validity in medically ill populations (34). The measure contains seven anxiety items and seven depression items, which correspond to two subscales (anxiety and depression). For each item, the participant is asked to identify how much a given statement is applicable (*Most of the time, A lot of the time, From time to time, Occasionally or Not at all*). A cut score of 8 identifies cases of anxiety and depressive disorders for each subscale, resulting in sensitivity and specificity of approximately .80 (34). In a study of screening for depression in patients with head and neck cancer, the HADS demonstrated the highest absolute levels of sensitivity, specificity, and positive predictive values for identifying cases of Major and Minor Depression compared to other commonly used measures of depression [30]. It has also been found to be a useful for screening for both anxiety, depression and general psychological distress in this specific population [31].
- II. Symptom burden
 - a. The Memorial Symptom Assessment Scale Short Form (MSAS-SF; [32]) is a multidimensional symptom assessment instrument. It assesses both symptom presence and symptom distress. It assesses the occurrence of 26 physical symptoms and four psychological symptoms on a scale from 0 (“no symptom”) to 4 (“very much”). Distress is rated on a 5-point scale including not at all, a little bit, somewhat, quite a bit, and very much. The scale yields a total symptom distress score (TMSAS), a global distress index (GDI), a physical symptom distress score (PHYS), and a psychologic symptom distress score. (PSYCH) In a sample of patients with cancer, Cronbach alpha was 0.80 for the GDI, 0.82 for the

PHYS, and 0.76 for the PSYCH, and 0.87 for the TMSAS. It also demonstrated good criterion validity in patient with cancer.

III. Health-related quality of life

- The Functional Assessment of Cancer Therapy - Head and Neck Version (FACT-HN) is a 27-item self-report instrument designed to assess quality of life for patients with HNC (35). Items assess four domains: physical, social/family, emotional, and functional well-being as well as specific items assessing head and neck symptoms. The scale uses a Likert-type scale (0 to 4) to produce subscale and total scores with higher scores indicating higher quality of life. It is a reliable, valid measure of quality of life for patients with head and neck cancer (35).

IV. Intervention use

- Participant reported acceptance of the intervention will also be assessed via time line follow-back (TLFB; (38)). Participants will be given a TLFB measure in order to ascertain a retrospective, calendar-based, daily estimate of use of the intervention materials. This will be sent to participants via a HIPAA secure REDCap link. Study staff will contact participants who do not return their TLFB data in order to administer the recall via telephone.

V. Anxiolytic use

- Participant use of anxiolytic medications will be assessed through both medical record review of prescriptions and patient reported use. All participants will record their use of any of the following medications: alprazolam, bromazepam, chlordiazepoxide, clonazepam, clorazepate, diazepam, flurazepam, and lorazepam. All participants will be given a TLFB measure to track daily use of anxiolytics during the course of the study. This will be administered via a HIPAA secure REDCap link. Participants who do not return their TLFB data will be contacted by study staff in order to administer the recall via telephone. The TLFB is a reliable measure of patient-reported substance use (i.e., cigarettes, cannabis, and alcohol).

Following study participation, participants in the intervention condition will be invited to participate in a qualitative interview. The interviews will be conducted by the study investigator, [name] or by the research study assistant who will be appropriately trained in qualitative methodology. Qualitative data regarding acceptability of the intervention will be gathered through one-on-one, standardized open-ended interviews. Interviews will be conducted using a semi-structured interview protocol (37), which will be given either in person or over the telephone. The interview will be recorded, after obtaining consent to do so by the participant, so that it can be transcribed and analyzed appropriately. Interviews will last approximately 30 minutes.

7.3 STUDY SCHEDULE

7.3.1 SCREENING

Screening Visit: Day 1

The research study assistant will review medical history to determine eligibility based on inclusion/exclusion criteria prior to approaching the potential participant. Study personnel will inform the patient's treating physician and Radiation Oncology charge nurse and confirm eligibility.

Eligible participants will then be presented with study parameters.

7.3.2 ENROLLMENT/BASELINE

Enrollment: Day 1

Enrollment will generally occur on the same day as the Screening visit. However, interested patients can enroll in the study in the time between the Screening visit and CT simulation. There will be two possible routes for consent:

1. Participants may provide verbal consent for screening and baseline procedures only, and will provide a signed full consent prior to other study procedures (in person or via e-consent).
2. Informed consent and authorization for the entirety of the study will be obtained at the time of screening/baseline through an e-consent process. Signatures may be obtained via REDCap, mail, e-mail with scanned document or picture of the signed consent, or by bringing the signed consent and authorization into the clinic. All questions will be answered by the study personnel and/or treating physician

Study personnel will then complete the enrollment portion of the REDCap survey with the patient, which will include information regarding the patient's date of birth and email address. Additional information documenting the date of the informed consent as well as the consenting study personnel will also be collected.

The participant will complete study baseline measures and then will be randomized to either the intervention of treatment as usual condition. Participants may complete baseline measures any time after consenting and before the CT simulation visit.

7.3.3 FOLLOW-UP

Participants randomized to the intervention condition will complete two in-person or virtual (telephone or secure videoconference) guided imagery sessions. The first will be during the week of the CT simulation visit and the second during the first week of RT (See Table 1).

Table 1. Intervention schedule

Guided Imagery Session	Time	Session Aims
Session 1	During the week of CT simulation	
 • Introduction to guided imagery • Selection of guided imagery vignette • In-session delivery of vignette • Planning for use of guided imagery
Session 2	During first week of RT	
 • Review of guided imagery use • Selection of new vignette if necessary • Addressing barriers to guided imagery use

Patients will then be able self-administer the GI both before and during RT throughout their treatment. Follow-up data for all participants will be collected during the third week (or halfway point) of RT, following completion of RT, and approximately one month following completion of RT. All participants will complete weekly self-assessment of anxiolytic medication use. Intervention participants will complete weekly assessments of guided imagery intervention use. See Table 2 below for schedule of data collection.

Table 2. Assessment schedule for study participants

Construct	Measure	Baseline & Prior to RT	Week 1	Week 2	Week 3	Week 4	Week 5	Week 6	Week 7	Week 12
Anxiety	HADS-A	X	X		X				X	X
Depression	HADS-D	X	X		X				X	X
Symptoms	MSAS-SF	X			X				X	X
Health-related QOL	FACT-HN	X			X				X	X
Intervention use*	TLFB-I	X	X	X	X	X	X	X	X	
Anxiolytic use	TLFB-A	X	X	X	X	X	X	X	X	
Demographics		X								

* Guided imagery participants only

HADS-A = Hospital Anxiety and Depression Scale – Anxiety Subscale; HADS-D = Hospital Anxiety and Depression Scale – Depression Subscale; MSAS-SF = Memorial Symptom Assessment Scale – Short Form; FACT-HN = Functional Assessment of Cancer Therapy – Head and Neck Version; TLFB-I = timeline follow-back for intervention use; TLFB-A = timeline follow-back for anxiolytic use

7.3.4 FINAL STUDY VISIT

Following completion of the Week 12 study assessment measures the participant will connect with the study research assistant either in person or by telephone. Treatment as usual participants

will be provided with an MP3 player containing the guided imagery audio files either in person or by mail. Intervention participants will be asked to participate in a 30-minute qualitative interview assessing the acceptability and feasibility of the intervention. This visit, once scheduled, will be the final study visit.

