- **Primary Endpoint:**
Acceptability and feasibility of guided imagery intervention assessed through self-reported intervention use and qualitative interviews with intervention participants
- **Secondary Endpoints:**
Self-reported anxiety and depression at one month after completion of radiotherapy as measured by the Hospital Anxiety and Depression Scale
- **Tertiary/exploratory:**
Self-reported use of anxiolytic medications as measured by timeline follow-back methodology. We will also measure health-related quality of life in patients receiving the intervention and treatment as usual.

Population:

- **Sample size**
 - Maximum number of participants that can be enrolled is 72 (allow for screen failures)
 - Minimum number of participants to be enrolled 50 (number of participants needed to answer scientific question/aims)
- **Gender** Male and Female
- **Age Range** 18-100
- **Demographic group** Ambulatory outpatients receiving radiotherapy for head and neck cancer

- **General health status** Initiating radiotherapy for head and neck cancer

Number of Participating Sites enrolling participants:

[figure not shown]
1 (University of Colorado Cancer Center)

Description of Study

Agent: Guided imagery

Study Duration: 2 years

SCHEMATIC OF STUDY DESIGN

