4.2 STUDY ENDPOINTS

4.2.1 PRIMARY ENDPOINT

The primary endpoint of the study is the feasibility and acceptability of the guided imagery intervention for anxiety and depression related to radiotherapy. Feasibility and acceptability will be assessed following study participation through both qualitative and quantitative methods. Feasibility of intervention use will be assessed through rates of study enrollment and GI session attendance. It will also be assessed through self-reported use of the GI intervention measured through timeline follow-back. Acceptability of the intervention will be assessed through qualitative interviews with intervention participants. The interviews will assess participant experience in the intervention including thoughts about the intervention content and structure of the intervention.

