7.3.5 EARLY TERMINATION VISIT

If the participant chooses to terminate participation early, he or she will be contacted either in person or by phone to verify the decision to discontinue participation. This decision will be documented by research personnel.

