7.4 SCHEDULE OF EVENTS TABLE

	Screening & Enrollment	Prior to RT	During Radiation Therapy (RT)							Post-RT
	Baseline	CT Simulation Visit	Week 1	Week 2	Week 3	Week 4	Week 5	Week 6	Week 7	Week 12
Consent	X									
Eligibility ¹	X									
Demographics	X									
Randomization ²	X									
CT Simulation		X								
In-Person or virtual GI Session		X	X							
Patient self-administered GI use ³			X	X	X	X	X	X	X	
Anxiety HADS-A	X		X		X				X	X
Depression HADS-D	X		X		X				X	X
Symptoms MSAS-SF	X				X				X	X
Health-related QOL FACT-HN	X				X				X	X
Intervention use TLFB-I ³		X	X	X	X	X	X	X	X	
Anxiolytic use TLFB-A		X	X	X	X	X	X	X	X	
Research Assistant Contact for F/U ⁴										X
Qualitative Interview ⁵										X

*Patients may complete the assessments for weeks 1, 3, 7 and 12, listed above any time during the specified week (7 days) of treatment, with Day 1 being defined as the first day of radiation treatment. TLFB measures may be completed at any time.

1. Determined by chart review and confirmation of eligibility between research study personnel and treating physician.
2. Upon completion of baseline measures.
3. Guided imagery (intervention) participants only.
4. Following completion of 12-week study measures, in person or on the phone:
Treatment as usual participants will be provided with an MP3 player containing the guided imagery audio files either in person or by mail.
Intervention participants will be offered the opportunity to participate in a 30-minute qualitative interview assessing the acceptability and feasibility of the intervention.
5. The qualitative interview may be conducted via phone or in person following completion of the Week 12 study assessments.

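### The acceptability interview is scheduled only after the Week 12 measures, and guided imagery participants who leave early have no stated route to one

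*Combined protocol and SAP*

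**What the plan says.** The synopsis defines the primary endpoint as "Acceptability and feasibility of guided imagery intervention assessed through self-reported intervention use and qualitative interviews with intervention participants". Section 4.2.1 assigns acceptability to the interviews and describes their content: "The interviews will assess participant experience in the intervention including thoughts about the intervention content and structure of the intervention".

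On timing, the sections differ in how specific they are:

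- Section 7.1 is general: "Following study participation, participants in the intervention condition will be invited to participate in a qualitative interview". Section 4.2.1 likewise places the assessment after study participation and does not mention Week 12.
- Section 7.3.4 ties the contact at which the invitation is made to the last assessment: "Following completion of the Week 12 study assessment measures the participant will connect with the study research assistant either in person or by telephone".
- Section 7.4 marks the interview only in the Week 12 column. Footnote 4 says the same as 7.3.4, and footnote 5 reads: "The qualitative interview may be conducted via phone or in person following completion of the Week 12 study assessments".

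For a participant who leaves early, Section 7.3.5 says that "he or she will be contacted either in person or by phone to verify the decision to discontinue participation", and that the decision is documented. Section 5.4.2, on handling withdrawals, says only: "Participants will be informed in the consent process that they may discontinue the study at any time". Section 10.3.4 adds that staff will try to reach people who did not complete the study and ask the reason.

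**The concern.** Both therapist-led sessions are over by the first week of radiotherapy (RT) (Section 7.3.3, Table 1). A participant can therefore receive all the therapist-delivered GI, leave at any point in the following 11 weeks or so, and have no interview scheduled.

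If those who leave find GI less acceptable than those who stay, the themes will look too favourable. The plan's hypotheses are favourable ones (Sections 2.2 and 10.1), and the results are meant to inform larger studies and grant applications (Section 3), so the missing voices are those most able to contradict the expected finding. The saturation criterion in Section 10.3.2 would not expose this, because saturation can be reached entirely from people who stayed.

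**Working it through.** **Sections side by side.** The plan gives no figure for withdrawal or acceptability, so there is no stated result to reproduce. The first check is whether any section gives a leaver a route to an interview.

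| Section | What it provides for a GI participant who leaves before Week 12 |
|---|---|
| 4.2.1, 7.1 | Wording that could include leavers; no contact or timing set for them |
| 7.3.4; 7.4 footnotes 4 and 5 | Interview offer after the Week 12 measures |
| 7.3.5 | Contact to confirm and document the decision |
| 5.4.2 | No data collection |
| 10.3.4 | Attempted contact to ask the reason for dropout |

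None of them schedules an interview for a leaver.

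**What the other measures capture.** Section 7.1 says: "Participant reported acceptance of the intervention will also be assessed via time line follow-back". However, the timeline follow-back for intervention use (TLFB-I) records daily use and ends at Week 7 (Table 2). Session attendance is a count. A dropout reason is a retention item that Section 10.3.4 does not link to the thematic analysis in 10.3.2. In the planned analysis, none of these supplies views on content and structure.

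**A second, less certain group.** On a strict reading of 7.3.4 and 7.4, participants who stay but do not return the Week 12 surveys are also missed. Section 14.3 allows for uncompleted surveys, and Section 5.3 keeps the research assistant in contact with participants, so these people may be invited in practice.

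**Head counts.** Inputs:

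- GI arm n = 36 (Section 10.4), or 25 if the synopsis minimum of 50 is split equally (assumption).
- Withdrawal before Week 12, w = 5%, 10% or 20% (assumption).
- Leavers = n × w. Remaining = n × (1 − w).
- Leaver interviews gained if half accept (assumption) = 0.5 × n × w.
- Strict-reading group, if 10% of those remaining miss the Week 12 surveys (assumption) = 0.10 × n × (1 − w).

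| n | w | Leavers | Remaining | Gained if half accept | Strict-reading extra |
|---|---|---|---|---|---|
| 36 | 5% | 1.8 | 34.2 | 0.9 | 3.42 |
| 36 | 10% | 3.6 | 32.4 | 1.8 | 3.24 |
| 36 | 20% | 7.2 | 28.8 | 3.6 | 2.88 |
| 25 | 5% | 1.25 | 23.75 | 0.625 | 2.375 |
| 25 | 10% | 2.5 | 22.5 | 1.25 | 2.25 |
| 25 | 20% | 5.0 | 20.0 | 2.5 | 2.0 |

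Before refusals, the remaining 20.0 to 34.2 all exceed 12, the lower end of the 12 to 30 that Section 10.3.2 cites for saturation. The issue is who is interviewed, not how many. The leaver counts are upper limits on informative interviews, because they include anyone who left before a first session.

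**The case against.** The strongest reply is that Sections 4.2.1 and 7.1 set no completion condition. Participation also ends at withdrawal, so investigators could invite leavers without breaching either section. This stands as far as it goes: a reader might infer that the protocol excludes leavers by rule, and the documents do not support that. They leave the matter open in the general sections and schedule only stayers in the operational ones.

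It can also be said that limiting contact after withdrawal to confirming the decision and asking the reason is a defensible choice, and that the consent form, which was not available, may govern further contact. That is why any offer must depend on the consent wording and on the person's willingness to be contacted.

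There is further mitigation. A leaver who found GI unacceptable could say so when asked for the dropout reason. Session 2 reviews use and addresses barriers, and sessions are recorded (Sections 7.3.3 and 7.1). Those recordings are reviewed for fidelity, though, and are not planned as acceptability data. People who stop using GI but remain in the study can still be interviewed.

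Finally, no consequence is demonstrated. The output is thematic, no acceptability threshold is set, and Section 10.4 describes the study as preliminary. This limits the weight of the point but does not remove it.

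**Conclusion.** The point holds as a sampling gap in the interview component of the primary endpoint. Enrolment, session attendance and TLFB-I use do not depend on reaching Week 12, so the endpoint as a whole is not undermined.

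A reader might go further and conclude that the acceptability findings will be biased upwards. The documents do not support that. They give neither a withdrawal rate nor the reasons for leaving, so size and direction are both unknown. If people leave because of illness or treatment burden, there may be little or no bias. The head counts rest wholly on assumed withdrawal and survey-return rates and, for n = 25, an assumed equal split. The proper weight is a cheap improvement worth making.

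**What to change.** Align Sections 7.1, 7.3.4, 7.3.5 and 7.4 (footnotes 4 and 5) so that every participant randomised to GI who attended at least one GI session is invited to the interview, by telephone if preferred, whether or not Week 12 was completed. For leavers, make the offer at the early-termination contact (7.3.5) or the dropout contact (10.3.4), unless further contact is declined and subject to the consent wording. In Section 10.3.2, code these transcripts and the dropout reasons together with the other interviews. Report the numbers randomised to GI, invited and interviewed, by Week 12 completion status.

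Cost: wording in five sections (7.1, 7.3.4, 7.3.5, 7.4 and 10.3.2), possibly the consent form, and a few added interviews. Each takes about 30 minutes (Section 7.1) and a \$25 card (Section 5.3), plus 4 to 8 staff hours for scheduling, transcription and coding (assumption).

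- Low end, 0.625 interviews (n = 25, 5% withdraw, half accept): 25 × 0.625 = about \$16; 0.5 × 0.625 = 0.3 interview hours; 4 × 0.625 = 2.5 processing hours.
- High end with half accepting, 3.6 interviews (n = 36, 20% withdraw): 25 × 3.6 = \$90; 0.5 × 3.6 = 1.8 interview hours; 8 × 3.6 = 28.8 processing hours.
- Upper bound (n = 36, 20% withdraw, 10% of those remaining miss the Week 12 surveys, all accept): 7.2 + 2.88 = 10.08 interviews; 25 × 10.08 = \$252; 0.5 × 10.08 = about 5 interview hours; 8 × 10.08 = about 81 processing hours.

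Some leavers will decline, so the gap narrows but does not close. The reported counts let readers see what remains.
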